4.7.2 Lipid assessments

Lipids and lipoproteins will be assessed from laboratory data.

4.7.2.1 Methods of assessment

Patients must fast for at least 12 hours and have been sitting for at least 5 minutes before blood samples are taken for lipid analysis. If a patient attends for one of these study visits without having fasted (from 12 hours before) then they must be asked to return within the visit windows for their fasting blood sample.

Fasting concentrations of nonHDL-C, LDL-C, HDL-C and TC will be determined at Visits 1, 2 and 3. The following ratios will also be calculated at these visits: TC/HDL-C, LDL-C/HDL-C and nonHDL-C/HDL-C.

Fasting concentrations of apolipoproteins B and A-1 will be determined at Visits 2 and 3. The ApoB/ApoA-1 ratio will also be calculated at these visits.

The results of all lipid and lipoprotein levels measured at each visit will be revealed to the study centre personnel for randomisation.

All samples will be labelled with the patient initials, e-code and date of collection. A central laboratory will perform analyses of all laboratory samples. The central laboratory will be responsible for all lipid analysis and is certified for standardisation of lipid analysis by The College of American Pathologist. Further details of the central laboratory can be found in the central laboratory manual.

4.7.3 HDL-C assessment

HDL-C will be assessed by indirect precipitation method.

4.7.3.1 Methods of assessment

High Density Lipoproteins (HDL) can be separated by selectively precipitate low density and very low density lipoproteins (LDL and VLDL) adding Dextran sulphate in the presence of Mg++. In the remaining supernatant by centrifugation, which contains HDL can be then assay for cholesterol.

For further information please refer to the laboratory manual.

4.7.4 hsCRP assessment

hsCRP will be assessed from laboratory data.

4.7.4.1 Methods of assessment

hsCRP blood samples will be taken in the same conditions and the same moment than lipid blood samples.

hsCRP will be analysed at Visits 2 and 3.

4.8 Safety measurements and variables

The methods for collecting safety data are described below.

4.8.1 Adverse events

4.8.1.1 Definitions

The definitions of adverse events (AEs), serious adverse events (SAEs) and other significant adverse events (OAEs) are given below. It is of the utmost importance that all staff involved in the study is familiar with the content of this section. The principal investigator is responsible for ensuring this.

Adverse event

An adverse event is the development of an undesirable medical condition or the deterioration of a pre-existing medical condition following or during exposure to a pharmaceutical product, whether or not considered causally related to the product. An undesirable medical condition can be symptoms (e.g., nausea, chest pain), signs (e.g., tachycardia, enlarged liver) or the abnormal results of an investigation (e.g., laboratory findings, electrocardiogram). In clinical studies, an AE can include an undesirable medical condition occurring at any time, including lead-in or washout periods, even if no study treatment has been administered.

Serious adverse event

A serious adverse event is an AE occurring during any study phase (i.e., lead-in, treatment, washout, follow-up), and at any dose of the investigational product, comparator or placebo, that fulfils one or more of the following criteria:

- results in death
- is immediately life-threatening
- requires in-patient hospitalisation or prolongation of existing hospitalisation
- results in persistent or significant disability or incapacity
- is a congenital abnormality or birth defect
- is an important medical event that may jeopardise the patient or may require medical intervention to prevent one of the outcomes listed above.

The causality of SAEs (i.e., their relationship to study treatment) will be assessed by the investigator(s), who in completing the relevant case report form must answer "yes" or "no" to the question "Do you consider that there is a reasonable possibility that the event may have been caused by any of the following – study medication – other medication?". For further guidance on the definition of a SAE and a guide to the interpretation of the causality question, see Appendix B to the Clinical Study Protocol.

Note that SAEs that could be associated with any study procedure should also be reported. For such events the causal relationship is implied as "yes".

Other significant adverse events (OAE)

The Clinical Study Team Physician will identify OAEs during the evaluation of safety data for the Clinical Study Report. Significant adverse events of particular clinical importance, other than SAEs and those AEs leading to discontinuation of the patient from study treatment, will be classified as OAEs. Examples of these are marked haematological and other laboratory abnormalities, and certain events that lead to intervention (other than those already classified as serious), dose reduction or significant additional treatment. For each OAE, a narrative may be written and included in the Clinical Study Report.

4.8.1.2 Recording of adverse events

Adverse events will be identified at all visits except Visit 1 by means of a standard question, "Have you had any health problems since the previous visit?" The patient will be asked to provide a description of the event, the dates of onset and resolution, if any action was taken, the outcome and to assess the intensity of the reported adverse event according to the following scale:

- Mild: awareness of sign or symptom, but easily tolerated
- Moderate: discomfort sufficient to cause interference with normal activities
- Severe: incapacitating, with inability to perform normal activities

The investigator should make a causality assessment of the relationship of the event to the study drug and whether it constitutes an SAE or not (see Appendix B).

If a diagnosis of the patient's condition has been made, then the diagnosis should be recorded as the adverse event (e.g., fever, runny nose, cough can be recorded as "flu"). However, if a diagnosis of the patient's condition has not been made, or only if the individual symptoms are not well recognised, then the individual symptoms should be recorded separately.

It is important to distinguish between serious and severe AEs. Severity is a measure of intensity whereas seriousness is defined by the criteria in Section 4.8.1.1. An AE of severe intensity need not necessarily be considered serious. For example, nausea which persists for several hours may be considered severe nausea, but not a SAE. On the other hand, a stroke which results in only a limited degree of disability may be considered a mild stroke but would be a SAE.

AstraZeneca will classify events using National Medical Terminology Officially Accepted.

For screen failure patients, SAEs should be recorded from the time the patient consents to participate in the study up until the decision is made to discontinue the patient. Non-serious reports are not required for these patients.

For randomised patients, all adverse events and serious adverse events should be recorded from the time a patient consents to participate in the study up until discontinuation of study treatments. Patients should be instructed to report hospitalisations and any other medically serious events that occur within 30 days after last dosing of study treatment. The investigator should record these and any other serious events he is aware of in the 30-day period following discontinuation of study treatment, on the CRF and should report them to AstraZeneca in the usual manner.

After the initial AE/SAE report, the investigator is required to proactively follow the patient's condition. During the study all AE/SAEs should be followed-up until resolution, or until the condition stabilises and no further change is expected. AstraZeneca reserves the right to ask for further information on any adverse event that may be considered of interest.

Any SAEs ongoing at the final visit or reported within 30 days of study treatment discontinuation should be followed-up until resolution or until stabilised and no further change is expected.

Clinically significant abnormal laboratory values, vital signs or physical examination will not be recorded as adverse events unless:

- SAE criteria is fulfilled
- the patient discontinues the study due to the abnormality
- the investigator considers that the abnormality should be reported as an AE

However, if an abnormal laboratory value/vital sign is associated with clinical signs and symptoms, the sign/symptom should be reported as an AE and the associated laboratory result/vital sign should be considered additional information.

Should a pregnancy occur, it must be reported in accordance with the procedures described in Section 9.4, Procedures in case of pregnancy. Pregnancy in itself is not regarded as an AE unless there is a suspicion that an investigational product may have interfered with the effectiveness of a contraceptive medication.

Should an overdose (accidental or deliberate) occur, it must be reported in accordance with the procedures described in Section 9.3, Procedures in case of overdose, regardless of whether the overdose was associated with any symptom or not. All symptoms associated with the overdose should be reported as AEs.

4.8.1.3 Reporting of serious adverse events

Investigators and other site personnel must inform appropriate AstraZeneca representatives of any SAE that occurs in the course of the study **within 1 day** (ie, immediately but no later than the end of the next business day) of when he or she becomes aware of it.

The AstraZeneca representative will work with the investigator to compile all the necessary information and ensure that the AstraZeneca Drug Safety Department (ie, Clintrace Data

Entry Site) receives a report by **day one** for all fatal and life-threatening cases and by **day five** for all other SAEs.

The investigator must also reported follow-up information on SAEs within the same time frames.

If a non-serious AE becomes serious, this and other relevant follow-up information must also be provided to AstraZeneca within **1 day** as described above

All SAEs have to be reported, whether or not considered causally related to the investigational product. All SAEs will be recorded in the case report form. The investigator is responsible for informing the Ethics Committee and/or the Regulatory Authority of the SAE as per local requirements.

Subjects should be instructed to report hospitalisations and any other medically serious events that occur within 30 days after last dosing of study treatment. The investigator should record these and any other serious SAEs he is aware of in the 30-day period following discontinuation of study treatment, on the AE CRF page and should report them to AstraZeneca in the usual manner.

Any SAEs ongoing at the final visit or reported within 30 days of study treatment discontinuation should be followed up until resolution or until stabilised and no further change is expected.

4.8.2 Laboratory safety measurements and variables

4.8.2.1 Methods of assessment

Laboratory analysis will be performed at Visits 1, 2 and 3.

For visit 1, 20ml of blood will be needed. In this visit, lipid profile, glucose, HbA_{1c}, urea, creatinine, reduced hepatic profile (ALT, AST and GGT) and CK will be performed. A TSH analysis will be done and patients with levels ≥ 1.5 ULN will be excluded of the trial. β -HCG will be performed to women with childbearing potential at visit 1.

For visit 2 and 3, 10 ml of blood will be needed. In these visits, lipid profile, apolipoproteins, hsCRP, glucose, urea, creatinine, complete hepatic profile and CK will be performed.

A 10 mL mid-stream urine sample will be collected for analysis at the central laboratory at visits 2 and 3. It will consist of visual description (colour and appearance), a dipstick test (specific gravity, pH, protein (qualitative), haematuria, glucose, ketones, bilirubin and blood), microscopy (red blood cells, white blood cells, bacteria, casts and crystals.

In the event of elevated liver function tests, see Appendix D for guidance with regards to management of elevated liver enzymes.

In the case of new or increased symptoms of muscle pain/myopathy/elevation of CK to >5x ULN developing after randomisation, see Appendix E for guidance with regards to management of increased creatine kinase.

The volume of blood to be collected is detailed in section 4.9.

4.8.2.2 Derivation or calculation of outcome variables

The central laboratory (CARPERMOR) will perform all analysis.

Please refer to section 4.8.1.2 for details on how AEs based on laboratory assessments should be reported and recorded.

4.8.3 Vital signs and physical examination

4.8.3.1 Methods of assessment

Vital signs will be measured at visits 1, 2 and 3. This will include blood pressure, cardiac frequency and respiratory frequency.

The investigator will perform a full physical examination including weight and waist circumference at all visits. Height will additionally be measured at Visit 1.

4.8.3.2 Derivation or calculation of outcome variables

The patient should be requested to sit for 5 minutes before cardiac frequency; respiratory frequency and blood pressure are measured. These parameters will be recorded in the CRF.

4.9 Volume of blood sampling and handling of biological samples

The total volume of blood that will be drawn from each patient in this study is as follows:

Assessment		Sample volume (mL)	No. of samples	Total volume (mL)
Pharmacodynamic (lipid assays)		10	3	30
Safety	HbA1c	4	1	4
	Clinical chemistry	7.5	3	22.5
	TSH	5	1	5
Total				61.5 mL

Table 6Volume of blood to be drawn from each patient

In addition, 2 urine samples (10 ml volume per sample) will be collected over the course of the study.

The total volume of blood associated with the scheduled protocol visits should not exceed 61.5 mL. Additional samples may additionally be required if unscheduled visits are performed or repeats are necessary because of issues with storage/transportation etc.

The central laboratory will provide the investigational sites with all the appropriate materials for specimen collection and sample processing, packaging, and shipping to the central laboratory. The patient population in this study are not expected to be of a high infective risk, although there is a possibility that some high infective risk patients may be included. An investigator laboratory manual providing detailed instructions will be provided to each investigational site before the study starts.

A tourniquet may be applied, but for no longer than 2 minutes. Full details of sampling, sample preparation, and storage methods to be used are given in the investigator laboratory manual.

Samples, which will be analysed by the central laboratory, will be labelled according to the guidelines provided by the central laboratory.

Shipment of samples to the central laboratory will be carried out according to the guidelines provided by the central laboratory. The appropriate documentation should accompany the samples.

4.9.1 Analysis of biological samples

4.9.1.1 Clinical chemistry samples

The analyte stability limits defined by the central laboratory will be applied to all analyses performed on behalf of AstraZeneca. The central laboratory will not analyse samples that fall outside these stability limits. Analytical data will not be reported if found to have been derived from a sample that fell outside these stability limits. The standards of procedure followed by the central laboratory may be amended in accordance with its Standard Operating Procedures. The central laboratory will inform AstraZeneca of the stability limits relevant to this study before the first patient gives informed consent to take part in the study.

If the central laboratory chooses to sub-contract the analytical work to another laboratory, the central laboratory must assure itself and provide assurance to AstraZeneca that the other laboratory will apply defined stability limits to all analyses performed on behalf of AstraZeneca. Samples falling outside these limits must not be analysed or data reported. The other laboratory will inform AstraZeneca of the stability limits relevant to this study before the first patient gives informed consent to take part in the study.

4.9.1.2 Pharmacokinetic samples (Not applicable)

5. DATA MANAGEMENT

Case Report Forms (CRFs) will be provided for the recording of data. The forms will be in triplicate with carbonless paper. Data will be recorded legibly on the record forms in ballpoint pen. If any data is not available, omissions will be indicated on the record forms. Corrections should be legible, initialled and dated. Correction fluid or covering labels should not be used. The original top copy of the CRF will be collected and returned to AstraZeneca or its

designee, the second copy is for the monitor and the investigator will retain the third copy. It is important to ensure that all CRF entries are also legible on the retained copy.

Data collected from the completed CRFs will be entered into the clinical database. Laboratory data will be electronically transferred into the clinical database. The processes will be documented into the Data Management Plan and the validation performed under the direction of the responsible Data Manager, according to the Data Validation Manual.

Coding will be performed according to the National Medical Terminology Officially Accepted.

6. STATISTICAL METHODS AND DETERMINATION OF SAMPLE SIZE

6.1 Statistical evaluation – general aspects

Statistical analysis will be performed by statistical personnel outsourced by AstraZeneca in accordance with a comprehensive Statistical Analysis Plan (SAP) that will be prepared before unblinding of the data.

6.2 Description of outcome variables in relation to objectives and hypotheses

Each outcome variable relates to the corresponding objective as described in Section 4.7.

Primary efficacy outcome variable

1. Percentage change in TG levels from baseline to week 8.

Secondary efficacy outcome variables

- 1. Percentage change in non-HDL-C levels from baseline to week 8.
- 2. Percentage change in lipids and lipoproteins (different to TG and non-HDL-C) from baseline to week 8 (LDL-C, TC, HDL-C, ApoA1, ApoB, TC/HDL-C; LDL-C/HDL-C; nonHDL-C/HDL-C and ApoB/ApoA1 indexes).
- 3. Percent change of hsCRP from baseline to week 8.

Secondary safety outcome variables

1. Safety evaluation as determined by the incidence and severity of adverse events and abnormal laboratory values

6.3 Description of analysis sets

Efficacy

Efficacy data will be evaluated based on the intention-to-treat (ITT) and per-protocol (PP) populations.

The ITT population will consist of randomised patients who have a baseline reading and at least one post-baseline reading for at least one efficacy variable, and who have taken at least one dose of study medication. The PP population will consist of all patients in the ITT population who did not have a major protocol violation or deviations that would be likely to affect the efficacy outcomes (i.e. patients taking lipid lowering therapy other tan study drugs).

Patients will be evaluated using randomised treatment/dose (i.e., rosuvastatin 10 mg, rosuvastatin 20 mg, or placebo) for the ITT efficacy analyses, and actual treatment/dose received for the PP efficacy analyses.

For the test of superiority (versus baseline), the ITT population is the primary analysis population. Analyses of the ITT population will be performed using the last observation carried forward (LOCF) method and also using observed data. The LOCF analysis is the primary analysis. LOCF is defined as the last non-missing post-baseline value for a variable carried forward. If no non-missing value exists after baseline, the value will be treated as missing in the analysis. The analyses will be repeated for the PP population as a robustness check using only observed data. Any differences in interpretation of the results from the ITT population will be explored. For tests of no clinically significant deterioration from baseline the ITT and PP populations will be considered equally important.

Safety

The randomised safety population will consist of all patients who were randomised and took at least 1 dose of study medication. Safety data will be evaluated using actual treatment/dose received. In addition safety data from the lead-in period will be evaluated for all patients who enter the lead-in period.

The safety, ITT, and PP populations (including violations and deviations) will be determined prior to treatment unblinding.

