3.3.5.2 Incorrectly enrolled or randomised patients

Incorrectly randomised patients will continue to receive study treatment and assessment if, in the opinion of the investigator and/or study team physician, this is not consider to involve any risk or discomfort to the patient. There should be no attempt to switch treatments or change randomisation numbers.

If study medication is contraindicated, incorrectly randomised patients will be discontinue and contact to return study drug. However, the remaining visit and assessments most continue.

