3.3.5.3 Procedures for discontinuation

Patients who discontinue should always be asked about the reason(s) for their discontinuation and the presence of any adverse events. If possible, they should be seen and assessed by an investigator(s). Adverse Events (AEs) should be followed-up. Serious Adverse Events (SAEs)

should be followed-up until resolution or until the patient is lost to follow-up. All investigational products should be returned to the clinic by the patient.

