4.7.1.1 Methods of assessment

Patients must fast for at least 12 hours and have been sitting for at least 5 minutes before blood samples are taken for lipid analysis. If a patient attends for one of these study visits without having fasted (from 12 hours before) then they must be asked to return within the visit windows for their fasting blood sample.

Fasting concentrations of TG will be determined at visit 1, 2 and 3.

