6.5 Determination of sample size

The primary outcome variable for this study, which the sample size calculation has been based on, is the change in TG levels from baseline to Week 8.

Hypothesis testing will be undertaken to assess whether this change from baseline in TG levels is significantly different from zero (i.e., testing for a positive effect compared to baseline) for each of the rosuvastatin 10 mg and rosuvastatin 20 mg treatment groups. Similar hypothesis testing will also be performed for the placebo group.

No adjustment will be applied for the two rosuvastatin groups since the hypothesis testing in each of the treatment groups is independent. Therefore a 2-sided significance level of 5% will be applied for testing for a positive effect versus baseline. The required power is 90%.

Data taken from the literature suggest that an intervention with RSV will reduce TG levels between 22 and 25% average, with a maximum of 37% from baseline (expected p for sample 1(placebo):0.029; expected p for sample 2(RSV):0.229). We need a minimum of 67 fully evaluable patients per treatment arm to reach the 2-sided alpha 0.050 with a potency of 90% and a confident interval of 95%. Increasing sample size to 100 per arm increases potency to 97%.

As there are about 10 to15% patients that would probably not complete the 8 weeks treatment period (non-evaluable patients), we will increase the patients per treatment arm to 110 (a total of 330 randomised patients). As we have the facility of doing the trial in at least 10 centers, we can easily reach the target patients per treatment arm. Assuming a screen failure rate of 3:1 we will require approximately 990 patients to enter the study.

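### The primary ITT analysis uses LOCF, but only one post-baseline lipid sample is scheduled (week 8), so LOCF imputes nothing and patients without that sample drop out

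*Protocol*

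**What the plan says.** Section 6.3 of the protocol names the method outright: "The LOCF analysis is the primary analysis". Its definition reads "LOCF is defined as the last non-missing post-baseline value for a variable carried forward", followed by "If no non-missing value exists after baseline, the value will be treated as missing in the analysis". The same section also plans an observed-data analysis of the ITT population and a per-protocol analysis on observed data. To enter the ITT set a randomised patient needs a baseline reading, at least one dose, and "at least one post-baseline reading for at least one efficacy variable". Section 6.4.1.1 and the synopsis repeat that LOCF on ITT is primary.

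On sampling, section 4.7.1.1 states "Fasting concentrations of TG will be determined at visit 1, 2 and 3". Sections 4.7.2.1 and 4.7.4.1 put the other lipids at visits 1, 2 and 3, and the apolipoproteins and hsCRP at visits 2 and 3. Section 3.1 and Table 1 place visits 1 and 2 before randomisation, show no blood draw at visit 2.1, and make visit 3 at week 8 the final visit.

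On patients who discontinue, section 3.3.5.3 says "If possible, they should be seen and assessed by an investigator(s", and names no lipid sample. Section 6.5 expects about 10 to 15% of patients who "would probably not complete the 8 weeks treatment period (non-evaluable patients". By contrast, for incorrectly randomised patients taken off study drug, section 3.3.5.2 says that "the remaining visit and assessments most continue" (the verb is evidently meant as must).

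**The concern.** LOCF on an ITT set is normally read as a promise that patients who leave early still contribute to the primary result. Here the rule has no scheduled value to work on, and two other rules in section 6.3 remove the same patients: the ITT definition requires a post-baseline reading, and a value with nothing after baseline is left missing. The only remaining efficacy population, per-protocol, is a subset of ITT. So no planned efficacy analysis covers all randomised patients.

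What is at stake is the comparison of each rosuvastatin arm with placebo in section 6.4.1.1. Exclusion after randomisation can bias it if the reasons for leaving differ by arm or relate to week-8 triglycerides. The change from baseline within each arm then also describes a selected group. A sample that was never drawn cannot be recovered at analysis.

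**Working it through.** **Counting samples.** Triglycerides are measured at week -5 (visit 1), week -1 (visit 2) and week 8 (visit 3). Table 6 agrees, with three lipid samples per patient.
- Scheduled post-baseline samples: 1.
- Scheduled earlier post-baseline values available to carry to week 8: 1 - 1 = 0.

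The same count holds for the other lipids, the apolipoproteins and hsCRP. Under the schedule, the last post-baseline value is the week-8 value wherever one exists, so ITT-LOCF equals ITT-observed. A patient who enters ITT through another variable but has no triglyceride result is still missing for triglycerides.

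**Patients without a primary outcome.**
- From section 6.5: 330 × 0.10 = 33 and 330 × 0.15 = 49.5, or 11 to 16.5 per arm of 110.
- From section 3.1, with 285 to 300 expected evaluable: 330 - 300 = 30 and 330 - 285 = 45.
- Together: about 30 to 50 patients.
- On the percentages, 330 × 0.85 = 280.5 to 330 × 0.90 = 297 remain, or 93.5 to 99 per arm.

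**Is power affected?** Section 6.5 gives 0.029 and 0.229, two-sided alpha 0.05 and 90% power. Two-proportion formula, with d = 0.200 and mean proportion 0.129:
- n₀ = [1.960 × √(2 × 0.129 × 0.871) + 1.282 × √(0.029 × 0.971 + 0.229 × 0.771)]² / 0.200² = 56.9, so 57.
- With continuity correction: n = (n₀/4) × [1 + √(1 + 4/(n₀d))]² = 66.6, so 67. This reproduces the protocol's 67 per arm.
- Continuity-corrected power at 100 per arm is 98.4% (the protocol states 97%). At 93 per arm it is 97.6%, and at 99 per arm 98.3%.

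Power is therefore not the problem.

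**Illustration of possible bias.** This applies only if the planning proportions are read as percentage points of triglyceride reduction, which section 6.5 does not clearly say. The difference is then 22.9 - 2.9 = 20 points.
- If every rosuvastatin non-completer had a placebo-like week-8 value, the difference over all randomised patients would be 20 × 0.90 = 18 or 20 × 0.85 = 17 points.
- If non-completers respond like completers, it stays at 20 and nothing is overstated.
- Unequal dropout between arms could change the size or the direction.

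**The case against.** **LOCF is not strictly impossible.** Section 4.9 foresees extra samples at unscheduled visits, and section 3.3.5.3 hopes that patients who discontinue will be seen. A lipid value from either would be post-baseline, and the rule would carry it forward. This stands, so a reader who infers that nothing can ever be carried forward goes too far. But no such sample is planned or required, and its timing would be arbitrary.

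**The set is not strictly completers-only.** ITT membership requires a dose and a reading, not completed treatment. A patient who stops tablets but attends visit 3 counts, as randomised. This also stands. The defect is that only incorrectly randomised patients taken off drug are told to continue to that visit.

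**Bias in favour of rosuvastatin is not shown.** A reader might infer that poor responders leave and flatter the drug. No triglyceride value is scheduled between randomisation and week 8, treatment is blinded, and no criterion in section 3.3.5.1 concerns lipid response. Exits for adverse events, by choice or through loss to follow-up remain, but the documents do not link them to triglyceride response.

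**The SAP could settle it.** Section 6.1 promises a comprehensive SAP before unblinding, and imputation details belong there. However, the protocol itself fixes the primary method, its definition, the analysis set and the missing-value rule, and no SAP can supply week-8 samples that were not collected.

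**Conclusion.** The point holds in this form: under the planned schedule the primary LOCF rule imputes nothing, and the ITT set is a modified one, made up of randomised, dosed patients with a visit 3 sample. About 30 to 50 of 330 randomised patients could have no primary outcome, assuming that the protocol's non-completion rate applies and that those patients give no sample. The consequences are possible bias of unknown size and direction, and a label that overstates the protection against dropout.

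A reader might turn the illustration into a finding that the effect is overstated by 11 to 18% (20/18 = 1.11, 20/17 = 1.18). The documents do not support that. It needs every rosuvastatin non-completer to be placebo-like and the planning proportions to be triglyceride points. It also describes a mean, whereas the between-arm tests are Mann-Whitney. Nor is the trial underpowered on this account.

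**What to change.** **Section 3.3.5.3.** Ask every randomised patient who stops study drug to attend visit 3 at week 8 for the planned fasting sample, as section 3.3.5.2 already does for incorrectly randomised patients, and analyse the value in the randomised arm.

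**Section 6.3.**
- Delete LOCF as the primary method, or state that under the planned schedule it equals the observed-data analysis. Say how an early value from an unscheduled sample is handled.
- Define the primary set as all randomised patients with a baseline (visit 2) value, with no post-baseline requirement. The visit 2 triglyceride result is already an entry criterion, so this should be nearly everyone randomised.
- Add a sensitivity analysis for missing week-8 triglycerides, with details in the SAP. Placebo-based imputation is one option. Worst-rank imputation is another, and fits the planned Mann-Whitney test because that test uses ranks only.

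**Cost.** A short amendment and some follow-up effort, using a visit and a sample already in the schedule. The estimated effect may come out slightly smaller.
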